## 7. Statistical Methods

---

### 7.1 Study Subjects

#### 7.1.1 Disposition of Subjects

A subject is enrolled in the study when he/she signs and dates the Informed Consent, unless a full waiver of consent has been approved by the site's IRB or EC, meets all the inclusion/exclusion criteria, and is treated with at least one eligible Medtronic market released surgical product. A flow chart, tables, and/or listings may be used to summarize subjects' disposition.

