8.2. Subject Enrollment

Enrollment of a patient is complete once the Informed Consent Form (ICF) or the Data Release Form (DRF) and an Authorization, if applicable, have been obtained. The following data will be collected at Enrollment:

- Consent (DRF or ICF) signature and date

If consent is waived, or is not required by local regulations, refer to the Condition/Therapy Appendix for patient enrollment information.

Patients are to be enrolled within an enrollment window defined by the therapy received. Refer to the Condition/Therapy Appendix for specific enrollment criteria. It is the site's responsibility to maintain a log of all patients enrolled in the registry. A consent/enrollment tracking tool may be provided to sites to assist in tracking the attempts to enroll eligible patients.

Retrospective patient enrollment may be allowed in certain instances. Refer to the Condition/Therapy Appendix for more enrollment details, if applicable.

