10.12 Subject Exit, Withdrawal or Discontinuation

The rationale for patient exit should be documented in the patient's case history. Patients may be exited from the PSR under the following circumstances:

- Patient chooses to withdraw (e.g., consent withdrawal)
- PI deems withdrawal necessary (e.g., medically justified, failure of patient to maintain adequate registry compliance)
- Patient enrolled (signed ICF or DRF) prior to procedure or anticipated product use but procedure and/or product used not eligible for PSR enrollment
- All enrolled eligible products are inactive (e.g., electrical abandonment, product explant)
- Patient death
- Patient is no longer available for follow-up (i.e., lost to follow-up, refer to 10.6.4)

NOTE: If the patient is determined to be lost to follow up, documentation will be obtained, and the patient may be exited from the PSR. In addition, requirements set-forth by the Ethics Board must be followed by sites.

- Site closure
- Patient has completed PSR follow-up requirements

11. Risks and Benefits

There are no expected additional benefits or risks relative to participation in the PSR as data is being collected on routine medical care and all products are market-released. Products eligible for enrollment are market-released and should be used in accordance with approved labeling.

12. Adverse Events and Device Deficiencies

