Patients may be enrolled prior to or after the surgical or medical procedure. Whether a particular cohort under this CIP enrolls patients before or after surgery or both, is defined in the applicable analysis plan or addendum. The site will make every attempt to approach all eligible patients for enrollment and

Medtronic Business Restricted

perform a thorough review of the patient's medical record to ensure requested baseline and medical history information is complete. When enrolling a patient before surgery, procedures are recommended to occur within 30 days of consent. When enrolling a patient after surgery, it is recommended to do so within 30 days following the procedure. If deemed necessary, the study team is allowed to deviate from those 30 days before or following surgery, provided justification in the applicable analysis plan or addendum.

If the patient is enrolled into the registry prior to the surgical or medical procedure but the procedure is not completed with an eligible product, the patient will be exited from the registry. The data that is to be collected on patients exited early will include the Enrollment CRF and the Exit CRF at minimum. Other CRFs, if collected, will be defined in the applicable analysis plan or addendum. No data will be collected after the patient is exited. Vulnerable patient populations such as pediatric patients may be enrolled when the use of the device is approved in the population and region per the applicable instructions for use (IFU). Regional requirements will be followed and described in the applicable analysis plan or addendum.

Sites may submit to their Ethics Board for a full waiver of consent if applicable. Patients at sites where the Ethics Board *has not* granted a full waiver of consent are considered enrolled once informed consent has been obtained. Patients at sites where the Ethics Board *has* granted a full waiver of consent are considered enrolled once the patient's eligibility is assessed and verified and the Enrollment CRF is complete. Relevant enrollment data collected for eligible patients include but are not limited to:

- Eligibility verification (i.e. Section 8.3 Inclusion Criteria and Section 8.4 Exclusion Criteria).

Study activities (e.g., data collection and entry) can only start after the patient is enrolled in the study.

B.2 Baseline

The following types of data may be collected at baseline for enrolled patients regardless of procedure performed:

- Demographics
- Medical History

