#### 7.1.3 Analysis Sets

Subjects included in any analysis sets must consent to the PSR, unless a full waiver of consent has been approved by the site's IRB or EC, and meet all the inclusion/exclusion criteria. They must have been treated with at least one Medtronic market released surgical product. Additional inclusion/exclusion criteria include, but are not limited to specific components or models, time frame, data cutoff date and geography. For details, please refer to Analysis Plan (AP) or Addendum (AD).

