#### 7.9.1.3 Analysis Method

Event rate is calculated as number of events divided by number of units (e.g. subjects or product uses) where events are evaluated among subjects who have enrolled, met all the inclusion/exclusion criteria, and underwent surgical procedure. If there are more than one event per unit, only the first event is relevant to the primary objective.

Two-sided 95% confidence interval (CI) of the event rate will be calculated using Binomial distribution. All the events will be summarized in a table by Medical Dictionary for Regulatory Affairs (MedDRA)

terms. The number of events, and the number and percentage of subjects who experienced the event will be reported. Surgical or medical procedure related events and/or the product related events will be listed.

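### SAP 7.1.1 counts a subject as enrolled only once treated with an eligible product, while the protocol enrols at consent, so disposition in pre-surgery cohorts omits a required exit; SAP 7.1.3 also drops the word 'eligible'

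*SAP*

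**What the plan says.** **When a patient is enrolled**

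- Protocol 8.2 completes enrolment when the consent papers are in hand: "Enrollment of a patient is complete once the Informed Consent Form (ICF) or the Data Release Form (DRF) and an Authorization, if applicable, have been". Treatment is not a condition.
- Surgical Appendix B.1 repeats this for sites without a full waiver of consent. Under a full waiver, enrolment occurs when eligibility has been verified and the Enrollment CRF completed. B.1 allows enrolment before or after the procedure, with the timing set in the analysis plan (AP) or addendum (AD).
- The second inclusion criterion (Protocol 8.3, SAP 5.4.1) is met by a patient who is only intended to receive an eligible product.
- SAP 7.1.1 adds a condition. After consent (or a waiver) and eligibility, its text continues: "and is treated with at least one eligible Medtronic market released surgical product. A flow chart, tables, and/or listings may be used to summarize subjects'".
- Protocol 6.1 and SAP 5.1 also state, as a general design feature, that enrolment is limited to those treated with an eligible product.

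**What happens to patients who do not receive the product**

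- Protocol 10.12 lists this exit reason: "Patient enrolled (signed ICF or DRF) prior to procedure or anticipated product use but procedure and/or product used not eligible for PSR enrollment".
- Surgical Appendix B.1 requires the exit and specifies what is kept: "The data that is to be collected on patients exited early will include the Enrollment CRF and the Exit CRF at minimum". It stops data collection after the exit.

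**Who is analysed**

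- SAP 7.1.3, for any analysis set: "They must have been treated with at least one Medtronic market released surgical product". The word *eligible* is absent. Further criteria, including components or models, are left to the AP or AD.
- SAP 7.9.1.3, for the primary rate: "events are evaluated among subjects who have enrolled, met all the inclusion/exclusion criteria, and underwent surgical procedure".

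**The concern.** The protocol creates a class of patients who are enrolled before surgery and then exited because no eligible product was used. Under SAP 7.1.1 those patients were never enrolled. A disposition built on the SAP definition starts after they have gone, so it shows neither the exit nor the full number enrolled under the protocol. The reader cannot see how much selection took place between consent and treatment. That matters for a plan which states in SAP 6.2 that the registry sample represents the worldwide population.

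The missing word in SAP 7.1.3 is a second, smaller problem. SAP 5.3 says that not every Medtronic market-released surgical product is included, so non-eligible ones exist. A subject who received only such a product passes 7.1.3 as written, although the protocol exits that subject and collects nothing afterwards.

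**Working it through.** The plan has no figure for this point, so the main check is to apply the rules to each type of patient.

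**1. Patients enrolled before surgery.** All four types below have consented and meet the criteria. The last two columns apply 7.1.3 and 7.9.1.3 together.

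| Outcome after consent | Enrolled, Protocol 8.2 / B.1 | Enrolled, SAP 7.1.1 | Passes SAP 7.1.3 | In primary denominator, SAP meaning of *enrolled* | In primary denominator, protocol meaning |
|---|---|---|---|---|---|
| A. Eligible product used | yes | yes | yes | yes | yes |
| B. No procedure performed | yes | no | no | no | no |
| C. Surgery, no Medtronic surgical product | yes | no | no | no | no |
| D. Surgery, only a non-eligible Medtronic surgical product | yes | no | yes* | no | yes* |

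*Unless an AP or AD criterion on components or models removes the subject.

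**2. Disposition.** Types B, C and D are enrolled and exited under the protocol and absent from a SAP 7.1.1 count. In a cohort enrolled only after surgery, the product used is already known and this gap does not arise.

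**3. Which definition is operative.** The exit rules in Protocol 10.12 and B.1 make sense only if enrolment precedes treatment. B.1 also says study activities may start only after enrolment. Under SAP 7.1.1, baseline collection before surgery would come before enrolment. The statement in Protocol 6.1 and SAP 5.1 fits none of this.

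**4. Illustrative size of the disposition gap.** The SAP 6.1 formula reproduces its table. For a 10% rate and 5% half-width, 1.96² × 0.10 × 0.90 / 0.05² = 138.3, rounded up to 139. Take 139 patients enrolled before surgery and assume that a share f is exited because no eligible product was used:

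- f = 5%: 139 × 0.05 = 6.95, about 7 patients missing
- f = 10%: 139 × 0.10 = 13.9, about 14
- f = 20%: 139 × 0.20 = 27.8, about 28

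**5. Upper bound on the primary rate.** Suppose that *enrolled* in 7.9.1.3 has the protocol meaning, every exit is of type D, none has a recorded event, and no AP or AD criterion removes them. A true 10% would then be reported as 10% × (1 − f), which is 9.5%, 9.0% or 8.0% for f = 5%, 10% or 20%. Types B and C contribute nothing, so the real effect is smaller by an unknown amount. Under the SAP meaning it is zero.

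**The case against.** A reader might infer that the primary denominator depends on which definition of enrolment is used, and that untreated patients dilute the event rate. The documents do not support that in general. SAP 7.9.1.3 uses a term that SAP 7.1.1 has already defined, and the surgery condition adds to that definition; it does not replace it. Even with the protocol meaning, 7.1.3 bars from every analysis set anyone not given a Medtronic surgical product. Only type D could enter, and a product-specific AP or AD could exclude that group by model. Those documents are not available here. This objection stands, and it limits the denominator question to a wording risk.

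A reader might also infer that the SAP makes it impossible to show the exit. That goes too far. SAP 7.1.1 leaves the form of the disposition open, nothing forbids a flow chart that starts at consent, and the Enrollment and Exit CRFs are collected in any case. What remains is that the stated definition excludes these patients and nothing in the SAP requires them to be shown.

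It is also fair to say that SAP 7.1.1 did not invent its definition, since Protocol 6.1 says much the same. That makes the protocol inconsistent with itself; it does not reconcile 7.1.1 with the operative rules in 8.2, 10.12 and B.1. Finally, this is a platform SAP that defers detail to addenda. That would answer a silence, but here a stated rule conflicts with the protocol.

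**Conclusion.** The conflict is real. SAP 7.1.1 requires treatment, Protocol 8.2 and Surgical Appendix B.1 do not, and Protocol 6.1 and SAP 5.1 contradict those operative rules. In cohorts enrolled before surgery, a disposition of SAP-enrolled subjects omits the exit for no eligible product used and understates the number enrolled. SAP 7.1.3 separately admits a subject given only a non-eligible Medtronic product, unless an AP or AD criterion excludes that subject.

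The size is unknown because no exit share is given; the 7 to 28 in 139 rests on an assumed 5% to 20%. The primary rate is unaffected on the SAP's own definition. The 9.5%, 9.0% and 8.0% figures are upper bounds under assumptions the documents do not establish, and should not be read as an expected bias.

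**What to change.** 1. In SAP 7.1.1, adopt the protocol definition: enrolled at consent or data release, or at verified eligibility with a completed Enrollment CRF under a full waiver. Reconcile Protocol 6.1 and SAP 5.1 with it.
2. For cohorts enrolled before surgery, report the numbers enrolled, treated with an eligible product, and analysed, with the exit for no eligible product used as its own row.
3. Insert *eligible* in SAP 7.1.3.
4. In SAP 7.9.1.3, refer to the set treated with an eligible product. This must accompany step 1; otherwise the protocol meaning of *enrolled* would carry into the primary denominator and open the type D route that the SAP definition now closes.
5. State that the SAP 6.1 sample size counts treated subjects. If 139 were instead counted at consent, the assumed 5% to 20% exit share would leave about 132 to 111 treated. The half-width at a 10% rate would be 1.96 × √(0.09/132) = 5.12% to 1.96 × √(0.09/111) = 5.58%, against the intended 5%.

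The cost is SAP wording, one reconciling sentence in the protocol, and one more disposition row from CRFs already required. No new data are needed.

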#### 7.1.2 Clinical Investigation Plan (CIP) Deviations

If applicable, protocol deviations will be summarized by deviation type using counts and percentages.

#### 7.1.3 Analysis Sets

Subjects included in any analysis sets must consent to the PSR, unless a full waiver of consent has been approved by the site's IRB or EC, and meet all the inclusion/exclusion criteria. They must have been treated with at least one Medtronic market released surgical product. Additional inclusion/exclusion criteria include, but are not limited to specific components or models, time frame, data cutoff date and geography. For details, please refer to Analysis Plan (AP) or Addendum (AD).

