10.11 Deviation Handling

A deviation is defined as an event that did not occur according to requirements specific to regulations, CIP and/or associated AD. Examples include but are not limited to improper or incomplete ICF or DRF, patient did not meet eligibility criteria, etc.

Deviations will be reported and submitted to Medtronic each time a deviation occurs. The description of the deviation and justification must be documented and submitted to Medtronic.

Once a deviation has been identified it should be reported to Medtronic via CRF as soon as possible. Deviations may be identified through numerous sources, including but not limited to telephone conversations, site monitoring, patient record, or data review.

It is the site's responsibility to report deviations in compliance with their Ethics Board policies and/or local laws. For reporting requirements, refer to Table 3.

Medtronic is responsible for reviewing deviations and identifying any necessary corrective and/or preventive actions. Medtronic will determine whether any subsequent action is needed (e.g., amending the CIP or training). Repetitive or serious compliance issues may represent a need to initiate a corrective action plan and, in some cases, may necessitate suspending a site's ability to enroll until the problem is resolved.

Every attempt must be made to avoid registry deviations. If the PI and/or registry personnel anticipates, contemplates, or makes a conscious decision to deviate from PSR requirements, agreements or regulations, prior approval by Medtronic's registry team is required. In addition, prior approval is not necessary in situations where unforeseen circumstances are beyond the clinician's control.

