### 5.4.2 Exclusion Criteria

- Subject who is, or is expected to be, inaccessible for follow-up
- Subject is excluded by local law
- Subject is currently enrolled in, or plans to enroll in, any concurrent drug/device study that may confound the PSR results (i.e. no required intervention that could affect interpretation of all-around product safety and/or effectiveness)

Additional criteria may be required, refer to Condition/Therapy Appendix for further guidance.

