#### 7.9.1.2 Endpoint definition

The safety and performance of Medtronic market released surgical products is evaluated by the surgical or medical procedure related and/or the product related event rate. Depending on the follow-up schedule, the time for assessing the event rate varies. For products following the short-term schedule, the event rate is assessed post procedure or within 30 days post-procedure; for products following the long-term schedule, the time point for event rate assessment depends on the products.

In the case report form (CRF), the relatedness is collected as 4 categories: not related, possible, probable, and causal. For the primary endpoint, events classified as, 'possible', 'probable', 'causal' are considered related.

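### The SAP has no all-treated set, so reported events in treated patients with an eligibility deviation can be left out of every rate

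*SAP*

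**What the plan says.** SAP 7.1.3 sets one rule for all populations. It begins "Subjects included in any analysis sets must consent to the PSR", with an exception where a full waiver was granted, and adds "and meet all the inclusion/exclusion criteria". Treatment is a further condition: "They must have been treated with at least one Medtronic market released surgical product". It then lets an Analysis Plan or Addendum attach additional criteria.

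SAP 7.9.1.3 applies the same restriction to the primary analysis: "events are evaluated among subjects who have enrolled, met all the inclusion/exclusion criteria, and underwent surgical procedure". The endpoint is a safety rate; under SAP 7.9.1.2, safety and performance are "evaluated by the surgical or medical procedure related and/or the product related event rate". SAP 7.10 (Safety Evaluation) defines no population of its own and points back to 7.9.

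SAP 7.1.1 also builds eligibility and treatment into enrolment: besides consent, the subject "meets all the inclusion/exclusion criteria, and is treated with at least one eligible Medtronic market released surgical product". Protocol 8.2 does not; there, enrolment is complete once the consent or data release form and any authorization are obtained. Surgical Appendix B.1 says the same for sites without a full waiver. At sites with one, enrolment follows verification of eligibility and completion of the enrolment form.

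Protocol 10.11 gives "patient did not meet eligibility criteria" as an example of a deviation.

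**The concern.** The registry exists to describe how marketed products perform in ordinary use, and SAP 6.2 claims that its sample is representative of the worldwide population. For a safety rate with that purpose, the natural denominator is everyone who was exposed and whose data may lawfully be used. A consented patient who received an eligible product but failed another criterion is exposed, and any related events are reported. Under the SAP, neither the patient nor the events appear in any rate, and no sensitivity analysis would show whether this matters.

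The SAP also does not say when eligibility is judged for analysis. Some criteria are open to interpretation, for example "Subject who is, or is expected to be, inaccessible for follow-up", and Surgical Appendix B.1 allows enrolment after the procedure, so an event can precede the eligibility check. A reader of the final rate could not tell whether exclusions were settled without reference to outcome.

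**Working it through.** **Step 1. Can a treated, ineligible patient with events exist under the Protocol?**

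- Protocol 8.2: consent completes enrolment, with no eligibility condition.
- Protocol 10.11: failed eligibility is recorded as a deviation.
- Protocol 10.12: the exit reasons include use of a non-eligible procedure or product, but not failure of another criterion by itself. The investigator may still withdraw a patient.
- Surgical Appendix B.5: procedure- and device-related events are reported when the site learns of them, apart from a list of unavoidable events.

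So such a patient can remain in the registry with reported events. SAP 7.1.2 would count the deviation by type, if applicable, but not the events.

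**Step 2. Which criteria matter?** SAP 5.4 lists six: consent or authorization, eligible product, enrolment window, inaccessibility for follow-up, exclusion by local law, and a confounding concurrent study. Consent and local law govern whether the data may be used, and the eligible product defines exposure; excluding on these is proper. Three remain: window, follow-up access and concurrent study. None is a clinical-risk condition.

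**Step 3. The plan's own figure.** SAP 6.1, for a 10% event rate and 5-point half-width:

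N = 1.96² × 0.10 × 0.90 / 0.05² = 0.3457 / 0.0025 = 138.3, rounded up to 139, as printed. All nine cells of that table reproduce.

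**Step 4. Illustration.** The documents give no frequency of eligibility failure and no event rate for such patients, so these are assumptions: 139 treated subjects, a 10% rate in eligible subjects, a share f ineligible, and a ratio R of the ineligible to the eligible rate.

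- All-treated rate = 0.10 × (1 − f + fR)
- Shift from the eligible-only rate = 0.10 × f × (R − 1)
- Subjects with an event left out = 139 × f × 0.10 × R
- Share of such subjects left out = fR / (1 − f + fR)
- Half-width after exclusion = 1.96 × √[0.09 / (139 × (1 − f))]

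| f | R | All-treated rate | Shift (points) | Left out | Share left out | Half-width (points) |
|---|---|---|---|---|---|---|
| 3% | 1 | 10.0% | 0 | 0.4 | 3.0% | 5.06 |
| 3% | 2 | 10.3% | 0.3 | 0.8 | 5.8% | 5.06 |
| 3% | 3 | 10.6% | 0.6 | 1.3 | 8.5% | 5.06 |
| 5% | 1 | 10.0% | 0 | 0.7 | 5.0% | 5.12 |
| 5% | 2 | 10.5% | 0.5 | 1.4 | 9.5% | 5.12 |
| 5% | 3 | 11.0% | 1.0 | 2.1 | 13.6% | 5.12 |
| 10% | 1 | 10.0% | 0 | 1.4 | 10.0% | 5.26 |
| 10% | 2 | 11.0% | 1.0 | 2.8 | 18.2% | 5.26 |
| 10% | 3 | 12.0% | 2.0 | 4.2 | 25.0% | 5.26 |

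At R = 1 the rate is unbiased and only events and a little precision are lost. If R were below 1 the shift would change sign; its limit, at R = 0 and f = 10%, is 0.10 × 0.10 × (0 − 1) = −1.0 point.

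**The case against.** The strongest reply is that restricting to pre-specified criteria defines a target population and is not in itself a bias, least of all in a single-arm registry with no hypothesis (SAP 7.9.1.2 and 7.9.1.1). That stands, and it is why the all-criteria set should be kept.

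Four stronger readings are tempting, and the documents do not support them.

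- **The rule removes higher-risk or off-label patients and so flatters the product.** The platform criteria contain no clinical-risk or labelling condition. An Analysis Plan or Addendum might add one, but none is available here.
- **Patients lost to follow-up would be reclassified as ineligible.** Loss has its own route in Protocol 10.6.4 and 10.12 and Surgical Appendix B.6, and eligibility is confirmed at baseline (Protocol 10.4). The gap is only that the SAP does not rule reclassification out.
- **The events are lost to surveillance.** Trend review (Protocol 10.9) and reporting to authorities (Protocol 16.8.2) are not tied to the SAP analysis sets. What is affected is the rate.
- **An all-treated set should simply replace the primary set.** Without a carve-out it would admit patients barred by local law. It would also mix in patients consented outside the window, whose late consent might itself follow a complication or depend on survival, and patients in a concurrent study that may confound the result.

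Two defences carry less weight. This is a platform SAP, and Protocol 6.2 lets an Addendum define its own cohort; but SAP 7.1.3 mentions those documents only as a source of further criteria, and SAP 3 makes its own method the default for any objective it covers. SAP 7.9.2 lists every death and device deficiency, but names no wider population, and a listing does not change a rate. The SAP 7.4 statement about using observed data concerns missing values.

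**Conclusion.** The point holds as a gap in the analysis sets. Read plainly, SAP 7.1.3 and 7.9.1.3 leave treated patients with an eligibility deviation out of every rate, although the Protocol allows them to stay in the registry and have events reported. This is a stated rule and not a detail left for later.

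Neither the direction nor the size of any bias can be read from the documents. Under the Step 4 assumptions the shift is at most 2 points, under half the narrowest planned half-width of 5 points, and it may be nil. The case for change does not rest on a demonstrated bias: a surveillance registry should be able to show its event rate in all exposed patients, and this SAP provides no way to do so.

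**What to change.** 1. In SAP 7.1.3, add a pre-specified all-treated safety set: valid consent or waiver, participation not barred by local law, and treatment with at least one eligible product.
2. In SAP 7.9.1.3 and 7.10, report the primary event rate and the safety tables in this set alongside the all-criteria set.
3. Show events in patients with eligibility deviations by deviation type, with patients consented outside the window shown separately. The reader can then judge late consent and concurrent-study participation.
4. State that eligibility is judged only on information at enrolment, so that later loss to follow-up or a later event cannot make a subject ineligible.
5. Align the definition of enrolment in SAP 7.1.1 with Protocol 8.2 and Surgical Appendix B.1.

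The cost is SAP wording and one repeated set of tables from data already collected. The all-treated rate may prove slightly less favourable.
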